6.2.3 Follow-up period and trial completion

End of Study visit

EoS visit should be conducted 28 days (+7 days) after the EoT visit for patients who have completed the trial on treatment as planned.

In exceptional cases, when the patient is not able to come at site for medical reason, the EoS visit can be replaced by a phone call.

If the EoT visit has been delayed and has been done 28 days or more after the treatment discontinuation, the EoS visit can be skipped.

The EoS should be conducted at week 156 for prematurely discontinued roll-over patients who were able to complete the remaining visits off-treatment until week 156 and at the overall end of the trial for new patients who prematurely discontinued trial treatment and were able to stay in the trial until the overall end of trial.

Observations and procedures:

- Adverse events, [REDACTED], concomitant therapy [REDACTED] since last visit will be reviewed and recorded.
- Physical examination including vital signs will be performed; weight and height will be repeated at follow-up in case of clinically relevant changes at EoT; data will be recorded in source documents and timely transferred per instructions provided (see ISF), to ensure central review as needed.
- Blood and urine samples will be repeated at EoS in case of clinically relevant changes at EoT.
- [REDACTED]
- Pregnancy test on urines will be conducted in female patients only. Test results will be documented in the patient's records.

[figure not shown]
If needed in the opinion of the investigator, after the EoS visit, additional visits may be scheduled for continued safety monitoring.

Abnormal assessments or lab values judged clinically relevant by the investigator will be monitored until they returned to a medically acceptable level.

Trial completion

The trial completion CRF page must be filled-in when the patient has terminated the trial. The trial completion (individual patient's end of trial) is:

- At the end of the EoS Visit for patients who have completed the trial on treatment as planned (including patients aged 21).
- At week 156, for roll-over patients who prematurely discontinued trial treatment before Visit 15 and were able to stay in the trial until week 156.
- At the overall end of the trial for new patients who prematurely discontinued trial treatment and were able to stay in the trial until the overall end of trial.
- At F-up/EoS visit, for roll-over patients who prematurely discontinued trial treatment before Visit 15 and were not able to stay in the trial until week 156 and for new patients who prematurely discontinued trial treatment and were not able to stay in the trial until the overall end of trial.
- At last contact, for other cases.

7. STATISTICAL METHODS AND DETERMINATION OF SAMPLE SIZE

As the main objective of this extension trial is to study long-term tolerability and safety, only descriptive statistics will be used. Some limitations due to the nature of the extension trial should be considered when interpreting the data (bias in the selection of the population, no comparative arm). All endpoints are considered exploratory only.

This statistical paragraph deals with the analyses to be performed on the extension trial only.

7.1 NULL AND ALTERNATIVE HYPOTHESES

[figure not shown]
No confirmatory testing is performed and hence no null and alternative hypotheses are defined.

[figure not shown]
7.2 PLANNED ANALYSES

7.2.1 General considerations

The following analysis sets will be defined for this trial:

- Treated Set (TS):
The Treated Set (TS) consists of patients who have received and taken at least one dose of open-label trial medication.

Adherence to the protocol will be assessed by the trial team. Important protocol deviation (iPD) categories will be documented in the DV domain template including protocol deviations relevant to the [REDACTED]. IPDs will be identified no later than in the final Report Planning Meeting, and the iPD categories will be updated as needed.

Patients will be analysed depending if and when they rolled-over from the parent trial (Group 1: New Patients [including patients who prematurely discontinued treatment permanently in 1199-0337, and completed patients from the parent trial not able to roll over into the extension trial within 12 weeks following their End of Treatment visit in the parent trial] and patients from 1199-0337 placebo arm Part A –, Group 2: patients from 1199-0337 Part B and from 1199-0337 nintedanib arm Part A) and overall.

Patients without any post-baseline data will be handled as missing for the respective endpoints and assessments (see [Section 7.3](#)).

Endpoints will be analysed for those patients where respective data is collected.

Further details will be specified in the TSAP.

7.2.2 Handling of Intercurrent Events

The expected intercurrent events of interest in this trial are:

- Treatment discontinuation

The strategies for handling intercurrent events in this trial are as follows:

While-on-Treatment: This is the effect of treatment while patients take it. Intercurrent events will be handled by default using the while-on-treatment approach as defined in ICH E9(R1), with the treatment period defined as the period from first trial drug administration to the end of the residual effect period following last administration. Any changes to background therapy or temporary discontinuations of trial drug will be considered part of the treatment regimen being assessed.

Each analysis will reference the strategy for handling intercurrent events that it will be estimating. The estimand for each main analysis in this protocol is the combination of the relevant detailed clinical objective from [Section 2.1](#) and this strategy.

7.2.3 Primary objective analyses

The primary endpoint listed in [Section 2.1.2](#) will be derived according to BI standards. The primary analysis refers to the number of patients with any treatment-emergent adverse event reported during the trial, i.e. all adverse events occurring between start of treatment and end of the REP. The analysis will be based on the TS and will be descriptive in nature.

As the primary objective of the study is to assess the tolerability and safety of nintedanib, please refer to [Section 7.2.6](#).

7.2.3.1 Sensitivity Analyses

No sensitivity analysis planned.

7.2.3.2 Subgroup Analyses

Subgroup analyses will be specified in the TSAP.

7.2.3.3 Supplementary Analyses

No supplementary analysis planned.

7.2.4 Secondary objective analyses

Not applicable.

7.2.6 Safety analyses

Adverse events will be coded using the Medical Dictionary for Drug Regulatory Activities (MedDRA). Standard BI summary tables and listings will be produced. All adverse events

with an onset between start of treatment and end of the REP, a period of 28 days after the last dose of trial medication, will be assigned to the on-treatment period for evaluation.

All treated patients will be included in the safety analysis. In general, safety analyses will be descriptive in nature and will be based on BI standards. No hypothesis testing is planned.

[figure not shown]
Statistical analysis and reporting of adverse events will concentrate on treatment-emergent adverse events, i.e. all adverse events occurring between start of treatment and end of the REP. Adverse events that start before first drug intake and deteriorate under treatment will also be considered as 'treatment-emergent'. The frequency of patients with AEs as well as incidence rates per 100 patient years will be presented.

Frequency, severity, and causal relationship of adverse events will be tabulated by system organ class and preferred term after coding according to the current version of the Medical Dictionary for Drug Regulatory Activities (MedDRA) at database lock.

Laboratory data will be analysed both quantitatively as well as qualitatively. The latter will be done via comparison of laboratory data to their reference ranges. Values outside the reference range as well as values defined as clinically relevant will be summarised. Patient groups will be compared descriptively with regard to distribution parameters as well as with regard to frequency and percentage of patients with abnormal values or clinically relevant abnormal values.

Vital signs, physical examinations, or other safety-relevant data observed at screening, baseline, during the course of the trial and at the end-of-trial evaluation will be assessed with regard to possible changes compared to findings before start of treatment.

[figure not shown]
Further details will be provided in the TSAP.

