Duration of treatment	
Treatment duration for each patient will be variable.
 
For roll-over patients: at least 3 years; or until alternative treatment options become or are made available (e.g., via marketing authorization, via compassionate use, or via similar process) to the patient outside of the clinical trial.
 
For new patients: until the overall end of the trial (with expected minimum treatment duration of 76 weeks).
 
Exception: patients aged 21 years must complete the trial before their 22nd birthday. Consequently, a treatment duration of at least 3 years might not be reached by some patients aged 21.
 
The overall end of trial will take place approximately when last roll-over patient is expected to reach 3 years of treatment (██████████) ensuring that nintedanib or alternative treatment options (e.g., via marketing authorization, via compassionate use, or via similar process) will be available for all remaining patients (roll-over or new patients) outside the trial at this time.

Statistical methods	
Descriptive statistics will be provided for adverse events (██████████).

FLOW CHART V1-V11

Trial Periods	Screening	Treatment ³																		
Visits	1 ¹	2	3 ⁴	3a ^{3&4}	4	4a ³	5	5a ³	6	6a ³	7	7a ³	8	8a ³	9	9a ³	10	10a ³	11	11a ³
Weeks ²	-4		2		12		24		36		52		64		76		88		104	
Days ²	≤28d before D1	D1 ²	15		85		169		253		365		449		533		617		729	
Time window for visits (days)		none	±3		±3		±3		±7		±7		±7		±7		±7		±7	
Informed consent and assent ⁵	X																			
HRCT sent to central review ⁶	X																			
Biopsy sent to central review ⁷	X																			
Demographics	X																			
Medical history	X																			
Baseline conditions ⁸	X																			
██████████	X ³⁰																			
Physical examination, Vital signs ⁹	X	X	X		X		X		X		X		X		X		X		X	
Height (standing and sitting) ¹⁰	X	X			X		X		X		X		X		X		X		X	
Leg length		X			X		X		X		X				X				X	
Weight ¹⁰	X	X	X		X		X		X		X		X		X		X		X	
12 lead-ECG (at rest) ¹¹	X	(X)					X				X				X				X	
Safety Laboratory (blood and urine) ¹²	X ⁹	X	X	(X)	X	(X)	X	(X)	X	(X)	X	(X)	X	(X)	X	(X)	X	(X)	X	(X)
Pregnancy tests ¹³	X	X	X		X		X		X		X		X		X		X		X	
Dispense urine pregnancy test with Diary Card (if applicable) ¹³		X ¹³	X ¹³		X		X		X		X		X		X		X		X	
Review Diary Card for urine pregnancy test (if applicable) ¹³					X		X		X		X		X		X		X		X	
██████████		X			X		X		X		X									

Trial Periods	Screening	Treatment ³																		

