For all patients, during treatment period, dose is adjusted based on patient's weight. Dose reduction to the next lower dose is possible to manage adverse events. The lowest possible dose is 25 mg b.i.d. (50 mg daily).

Roll-over patients will be requested to stay in the trial for at least 156 weeks (until Visit 15). At week 156, roll-over patients who can be treated with nintedanib or alternative treatment options outside the clinical trial will have their EoT Visit instead of Visit 15.

The remaining roll-over patients will continue in the trial until nintedanib or alternative treatment options can be made available to them outside the clinical trial.

New patients will be requested to stay in the trial until the end of trial (with expected minimum treatment duration of 76 weeks), then patients will perform their EoT Visit and enter in the 28-days follow-up period off-treatment until End of Study Visit (EOS).

Exception: patients aged 21 years must complete the trial before their 22nd birthday. Consequently, a treatment duration of at least 3 years might not be reached by some patients aged 21.

Patients completing trial while being 21 years old, even with a treatment duration less than 3 years, will be considered as completed patients.

The overall end of trial will take place approximately when last roll-over patient is expected to reach 3 years of treatment () ensuring nintedanib or alternative treatment options (e.g., via marketing authorization, via compassionate use, or via similar process) will be available for all remaining patients (roll-over or new patients) outside the trial at this time.

At this time, all the remaining patients will perform their EoT Visit. For logistical reasons, it may be planned that EoT visit of all remaining patients will occur within 6 weeks before the planned date of Visit 15 of last roll-over patient. If regular scheduled visit is planned for a patient during this period of 6 weeks, then the patient will skip this regular visit and will perform directly the EoT visit instead. After the EoT visit, all remaining patients will enter a 4-week follow-up period.

Trial medication will be stopped prematurely if a reason for withdrawal is met (refer to [section 3.3.4](#)).

Roll-over patients will be considered as prematurely discontinued from trial treatment if they stop trial medication before week 156 (except at the age of 21).

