5.4.4 Liver enzyme and bilirubin elevations

Liver enzyme and bilirubin elevations will be reported using the following definitions:

- (ALT and/or AST ≥ 3 fold ULN) and bilirubin ≥ 2 fold ULN ^[1]
- ALT ≥ 5 fold ULN and/or AST ≥ 5 fold ULN
- ALT ≥ 3 fold ULN and/or AST ≥ 3 fold ULN

^[1] within a time window of 30 days i.e. the elevation of bilirubin should appear within 30 days after the elevation of AST and/or ALT

The proportion of patients presenting signs of hepatic injury will be summarised, based on the following definition for signs of hepatic injury:

- ALT and/or AST ≥ 8 fold ULN
- ALT and/or AST ≥ 3 fold ULN and total bilirubin ≥ 2 fold ULN ^[2]
- ALT and/or AST ≥ 3 fold ULN and unexplained INR > 1.5 ^[2]
- ALT and/or AST ≥ 3 fold ULN and unexplained eosinophilia ($> 5\%$) ^[2]

- ALT and/or AST ≥ 3 fold ULN and appearance of fatigue, nausea, vomiting, right upper abdominal quadrant pain or tenderness, fever and/or rash within +/- 7 days of the abnormal ALT and/or AST laboratory test result (please refer to [Table 10.5: 1](#) for the list of relevant MedDRA preferred terms to support the derivation of a potential hepatic injury)

^[2] in the same blood draw sample

In addition, maximum individual elevations based on worst value on treatment will be defined as:

- ≥ 3 fold ULN; ≥ 5 fold ULN; ≥ 8 fold ULN for AST and ALT and AST and/or ALT
- ≥ 1.5 fold ULN; ≥ 2 fold ULN for Bilirubin
- ≥ 1.5 fold ULN; ≥ 2 fold ULN for alkaline phosphatase (ALK)
- ≥ 3 fold ULN for Gamma-Glutamyl-Transferase (GGT)

Note: ULN refers to the Upper Limit of Normal from the central or local laboratory analysing samples.

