7. PLANNED ANALYSIS

Unless otherwise specified, all analyses described in this section will be done on the Treated Set. All available data (i.e. data for all available timepoints, as defined in [Section 6.7](#)) will be presented in the summary tables, irrespective if the timepoint is specified in the endpoint definition in the CTP. For endpoints with time intervals, only data for the intervals specified in the endpoint definition will be presented.

The labelling and display format of statistical parameters will follow BI standards (9). For End-Of-Text tables, the set of summary statistics is: N / Mean / SD / Min / Median / Max.

In descriptive statistics tables, mean, SD and median will be rounded to one additional digit than the raw individual value. For tables that are provided for endpoints with some extreme data, median, quartiles and percentiles should be preferred to mean, standard deviation, minimum and maximum.

Tabulations of frequencies for categorical data will include all possible categories and will display the number of observations in a category as well as the percentage (%) relative to the respective group (unless otherwise specified, all patients in the respective patient set whether they have non-missing values or not). The precision for percentages should be one decimal point. The category missing will be displayed only if there are actually missing values.

Unless otherwise specified, all analyses will be provided by patient group (initiated nintedanib or continued nintedanib) and overall (total):

[figure not shown]
- Group 1: Initiated nintedanib
 - New patients
 - Patients who prematurely discontinued treatment permanently in 1199-0337
 - Completed patients from 1199-0337 not able to roll over into the extension trial within 12 weeks following their End of Treatment visit in the parent trial (i.e. time period between last dose of trial drug in parent trial and first dose in extension trial is greater than 12 weeks)
 - Patients from 1199-0337 placebo arm Part A (i.e. from double-blind placebo arm who did not enter the open-label nintedanib period and only received placebo in the parent trial)
- Group 2: Continued nintedanib
 - Patients from 1199-0337 Part B (i.e. from open-label nintedanib period of the parent trial, time period between last dose of trial drug in parent trial and first dose in extension trial is less than or equal to 12 weeks)

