7.8.2 Laboratory data

7.8.2.1 Standard laboratory analyses

The analyses of laboratory data will be descriptive in nature and will be based on BI standards ([13](#)). The variables to be recorded are listed in Section 5.2.3 of the CTP.

Analyses of laboratory variables will be displayed by patient group and overall, over the whole trial. Please refer to [Table 6.7: 1](#) for time windowing definition.

For data received from the central laboratory the respective reference ranges will be provided in the ISF.

For INR measurements, no reference range is transmitted by the central laboratory, because the central laboratory does not have information on concomitant medication taken by the patients, and the reference range for INR depends on whether a patient is taking anticoagulants. The reference ranges for INR will therefore be imputed with 0.8 for the lower limit of normal (LLN) and with 1.2 for the ULN, which correspond to the reference range defined by the central laboratory for patients not taking anticoagulants and which is more conservative than the range for patients taking anticoagulants (LLN=2, ULN=3).

The estimated Glomerular Filtration Rate (eGFR) is calculated based on serum creatinine according to Schwartz formula in children and adolescent (2-17 years old) and according to CKD/EPI formula in adults (see CTP Sections 5.2.3 and 10.3). As the parameter (eGFR) evaluated is the same and just the formula are chosen appropriately as recommended per age, for the analyses these two methods of calculation are considered to result in the same parameter.

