7.8.2.2 Liver enzyme and bilirubin elevations

A thorough description of liver enzymes and bilirubin elevations, as defined in [Section 5.4.4](#), will be given over the whole trial by patient group and overall, including:

[figure not shown]
- Summary table of liver enzyme elevation
- Summary of signs of hepatic injury (see [Section 5.4.4](#))
- Summary table of individual maximum liver enzyme and bilirubin elevations
- Time to first onset and number of patients with liver enzyme elevation. The time to onset of first liver enzyme and bilirubin elevation [days] will be summarised according to both, quartiles from Kaplan-Meier curve
- Kaplan-Meier plot of time to first liver enzyme elevation. No statistical test will be performed. Separate plots will be presented by patient group and overall.
- Single time course profiles of liver enzymes and other laboratory parameters (ALT, AST, alkaline phosphatase, total bilirubin, eosinophils/ leukocytes, GGT) for all patients (maximum individual elevations given in [Section 5.4.4](#)).
- Graphical displays of potential Hy's law cases

[figure not shown]

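### Whole-trial percentages for signs of hepatic injury and worst laboratory values mix risk with observation length, because planned follow-up differs between the two patient groups

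*Protocol*

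**What the plan says.** - **Comparison.** For laboratory data, Protocol 7.2.6 states: "Patient groups will be compared descriptively with regard to distribution parameters as well as with regard to frequency and percentage of patients with abnormal values". It extends this to clinically relevant abnormal values.
- **Hepatic measures.** SAP 5.4.4 states: "The proportion of patients presenting signs of hepatic injury will be summarised". It also defines maximum elevations from each patient's worst on-treatment value: ALT and AST up to 8 times ULN, and separate thresholds for bilirubin, ALK and GGT. Under SAP 7.8.2.2 this description "will be given over the whole trial by patient group and overall".
- **Standard laboratory data.** SAP 7.8.2.1 states: "Analyses of laboratory variables will be displayed by patient group and overall, over the whole trial".
- **Denominator.** SAP 7 reports "the percentage (%) relative to the respective group", by default counting every patient in the set whether or not a value is missing.
- **Follow-up.** Protocol 3.1 states: "Roll-over patients will be requested to stay in the trial for at least 156 weeks". New patients stay "until the end of trial (with expected minimum treatment duration of 76 weeks").
- **Groups.** SAP 7 analyses initiated against continued nintedanib. Group 1 is new patients, those handled as new, and roll-overs who received only placebo in Part A of the parent trial. Group 2 is roll-overs from Part B or from the Part A nintedanib arm.
- **Existing time adjustment.** SAP 7.8.1.2 gives adverse event rates per 100 patient-years. SAP 5.4.4.1 and 7.8.2.2 give Kaplan-Meier analyses by group for ALT/AST at 3 times ULN, at 5 times ULN, and at 3 times ULN with bilirubin at 2 times ULN.

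**The concern.** The proportion of patients who have ever met a threshold rises with time observed and with the number of samples taken. When two groups are followed for different lengths by design, their whole-trial proportions reflect that difference as well as any difference in risk. The plan allows for this in adverse events and in three liver endpoints. The visible SAP does not allow for it in the derived signs of hepatic injury, in the remaining worst-value categories, or in any whole-trial percentage with abnormal laboratory values. These tables sit side by side by group, and the contrast between initiating and continuing treatment is where an early hepatic signal should appear. A reader could see an excess that is only longer observation, or miss a real early excess in initiators.

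**Working it through.** The documents give no event rate, power or event count, so there is no planned figure to reproduce. All rates below are assumptions, shown as a range.

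**Inputs**
- Treatment of 76 weeks (new patients, expected minimum) and 156 weeks (roll-overs): Protocol 3.1.
- On-treatment window to last intake plus 28 days, so 4 weeks are added: SAP 7.8.
- Recruitment of new patients over 18 months: Protocol 3.3. This is 18 x 365.25 / 12 / 7 = 78 weeks, so their treatment is assumed evenly spread from 76 to 76 + 78 = 154 weeks.
- Share of Part A placebo roll-overs in Group 1: not given; 10 to 30% assumed, each followed like Group 2.

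**Step 1: equal constant rate in both groups.** Expected percentage = 1 - exp(-rate x weeks x 7/365.25).

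At 10 per 100 patient-years without the residual period: 1 - exp(-0.10 x 76 x 7/365.25) = 13.6% and 1 - exp(-0.10 x 156 x 7/365.25) = 25.8%. These are the extremes. With the 4 weeks added:

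| Rate per 100 patient-years | New patients, all at 76 weeks | New patients spread over 76-154 weeks | Group 1 with 10-30% placebo roll-overs | Group 2 at 156 weeks |
|---|---|---|---|---|
| 2 | 3.0% | 4.5% | 4.6-4.9% | 5.9% |
| 5 | 7.4% | 10.8% | 11.1-11.8% | 14.2% |
| 10 | 14.2% | 20.3% | 20.9-22.1% | 26.4% |
| 20 | 26.4% | 36.4% | 37.3-39.2% | 45.8% |
| 40 | 45.8% | 59.2% | 60.4-62.7% | 70.7% |

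For the mixed column at a rate of 10: 0.9 x 20.3 + 0.1 x 26.4 = 20.9, and 0.7 x 20.3 + 0.3 x 26.4 = 22.1. The gap to Group 2 is 26.4 - 22.1 = 4.3 to 26.4 - 20.3 = 6.1 points.

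**Step 2: by number of samples.** The flow chart gives 7 post-baseline visits to week 76 (Visits 3 to 9) and 12 to week 156 (Visits 4 to 15). With a 2% chance per sample: 1 - 0.98^7 = 13.2% and 1 - 0.98^12 = 21.5%. These are again the two extremes of follow-up.

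**Step 3: risk concentrated early.** Protocol 1.2 says that in adults most hepatic events occur in the first three months. Assume initiators have 40 per 100 patient-years for 13 weeks and then a lower rate, and that continuing patients have only the lower rate.
- Lower rate 5, whole trial: initiators at 76 + 4 weeks, 1 - exp(-(40 x 13 + 5 x 67)/100 x 7/365.25) = 15.1%; continuers at 156 + 4 weeks, 14.2%. The tables look equal.
- Same hazards at a common 52 weeks: 1 - exp(-(40 x 13 + 5 x 39)/100 x 7/365.25) = 12.8% against 1 - exp(-5 x 52/100 x 7/365.25) = 4.9%. The early excess is visible.
- Lower rate 2, whole trial: 11.8% against 5.9%, so the order is the reverse of Step 1.

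**Step 4: effect of a common time.** With equal constant rates, Kaplan-Meier estimates at the same week, or rates per patient-year, have the same expected value in both groups. The crude percentages do not.

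**The case against.** Several points on the other side have force.

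- **Much is already covered.** Hepatic injury is an adverse event of special interest on the same laboratory criteria (Protocol 5.2.7.1.4), and laboratory findings judged clinically relevant are reported as adverse events (Protocol 5.2.3), so reported cases enter the patient-year rates. This stands in part. The SAP measure is derived from laboratory values plus a preferred-term list, not from investigator reporting, and the three Kaplan-Meier endpoints omit the 8-fold threshold and the INR, eosinophilia and symptom criteria. Exposure tables by group show the imbalance without adjusting for it.
- **The standard laboratory part is less certain.** SAP 7.8.2.1 defers to a sponsor standard that is not available here and refers to the visit windows in Table 6.7: 1. By-visit summaries would compare the groups at common times. That stands: for general laboratory abnormalities, the point applies only where whole-trial percentages are compared.
- **Follow-up overlaps.** New patients may stay well beyond 76 weeks. Group 2 can fall short of 156 weeks at age 21, when end-of-treatment visits are brought forward by up to 6 weeks, or after discontinuation. A reader might infer a 12-point gap from 13.6% against 25.8%, but those are extremes for new patients against roll-overs, and the analysed groups are not split that way.
- **Small numbers, no test.** If the 50 to 60 patients split evenly (an assumption), 4.3 to 6.1 points is about 0.043 x 25 = 1.1 to 0.061 x 30 = 1.8 patients per group. Protocol 7 calls all endpoints exploratory and warns of selection bias. This limits the consequence.
- **A common window does not equalise treatment age.** Group 2 has had nintedanib before its first extension dose. That also stands, and calls for a note beside the tables.

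**Conclusion.** The concern holds for the derived signs of hepatic injury and for the worst-value categories outside the three Kaplan-Meier endpoints, and conditionally for other whole-trial laboratory percentages. With an assumed equal constant rate of 10 per 100 patient-years, an assumed even spread of new patients over 76 to 154 weeks, and up to an assumed 30% placebo roll-overs in Group 1, that group would show about 20 to 22% against about 26%. The gap depends on these assumptions, none of which the documents fix.

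A reader might infer that continued treatment must look more toxic at equal risk. The documents do not support that: with the early adult hepatic hazard in Protocol 1.2, the whole-trial difference can cancel or reverse. What can be said is that size and direction are not interpretable without time adjustment. Because nothing is tested, the consequence is misreading of descriptive safety tables. This is a worthwhile, inexpensive improvement and not a flaw in the primary analysis.

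**What to change.** - **SAP 7.8.2.2:** extend the existing Kaplan-Meier method and the SAP 5.4.4.1 censoring rules to time to first signs of hepatic injury and to the worst-value categories. Report by-group cumulative estimates at weeks 52 and 76 from first extension intake.
- **SAP 7.8.2.1:** wherever whole-trial percentages with abnormal or clinically relevant abnormal values are compared by group, add the same common-time estimates, or first events per 100 patient-years using the SAP 7.8.1.2 time at risk. The common-time estimates are easier to interpret when risk is concentrated early.
- **Keep** the planned whole-trial percentages by group, with a note that follow-up differs and that Group 2 has prior nintedanib exposure.

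The cost is SAP wording and a few extra tables from data already planned, with no new assessments. The common-time estimates do not show later events, which remain in the whole-trial percentages.
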